6. COLLECTION OF STUDY VARIABLES

6.1 Recording of data

A Web Based Data Capture (WBDC) system will be used for data collection and query handling. The investigator will ensure that data are recorded on the eCRFs as specified in the study protocol and in accordance with the instructions provided.

The investigator ensures the accuracy, completeness, and timeliness of the data recorded and of the provision of answers to data queries according to the Clinical Study Agreement.

The investigator will sign the completed eCRFs. A copy of the completed eCRFs will be archived at the study site.

6.2 Study procedures

A study initiation visit must be conducted at the centre prior to the commencement of any study activities requiring informed consent. A schedule for the tests and evaluations to be conducted in this study is contained in this section and in [Table 1](#).

6.2.1 Screening procedures

The following assessments and procedures should be performed during screening Part 1 and Part 2 as per [Figure 1](#) and [Table 1](#).

For details of the schedule and nature of assessments see below:

- Date of birth, sex, race and ethnicity
- Medical and surgical history including previous cancer and radiotherapy and history of blood transfusions in previous 120 days

- Family history of cancer
- Current and concomitant medications including previous cancer therapies
- ECOG Performance Status
- Vital signs (supine blood pressure and pulse; body temperature), body weight, height
- Haematology /Clinical chemistry/Urinalysis
- Physical examination
- CT (or MRI if CT is contraindicated) of chest, abdomen and pelvis
- ECG (within 7 days prior to the start of the study treatment)
- Menopausal status; serum or urine pregnancy test for women of childbearing potential. The pregnancy test should be prior to performing the *BRCA* blood test during screening part 1, within 28 days prior to the start of study treatment and confirmed on day 1 prior to dosing
- For patients with **unknown** *BRCA* status: *BRCA1/2* mutation status. 2 blood samples: One blood sample to test for *BRCA* mutations using the current commercial Myriad *BRCA* analysis test, and the second blood sample for a bridging study to validate the companion diagnostic test for olaparib.
- Adverse events must be captured from time of consent. However, in Screening Part 1 of the study only SAEs related to study procedures will be collected. In Screening Part 2 all AEs/SAEs will be collected
- Archival paraffin embedded tumour tissue sample, if available
- Tumour biopsy (optional)
- EORTC QLQ-C30 should be completed prior to randomisation once eligibility is confirmed

The Principal Investigator/Sub-Investigator should adhere to the study plan, procedures and perform tests/observations in accordance with the protocol.

6.2.2 On treatment procedures

The visit schedule is based on 21-day cycles.

Patients will attend the clinic weekly on days 1 (1st day of treatment), 8 and 15, following the commencement of study treatment and then every 3 weeks (day 1 of every cycle) until discontinuation of treatment.

The following assessments will be performed at time points specified in the study schedule (see [Table 1](#)):

- Vital signs. Body weight is only required at day 1 of 1st day of study treatment, if it has not been assessed within 7 days of randomisation. Any other time as clinically indicated
- Haematology and clinical chemistry: Safety blood samples do not need to be repeated on Day 1 of study treatment if there have been separate assessments within 7 days before starting study treatment and which must have been 3 weeks after last dose of chemotherapy based therapy, unless the investigator believes that it is likely to have changed significantly
- Physical examination (assessments post Day 1 are not required to be captured on an eCRF, however any significant changes from baseline must be reported as an AE)
- CT of chest, abdomen and pelvis (or MRI if CT is contraindicated) performed until objective disease progression. RECIST assessments to be scheduled every 6 weeks (± 1 week) from randomisation for the first 24 weeks and then every 12 weeks (± 1 week). If progression is not confirmed by BICR an additional scan will be requested at the next scheduled visit. CT/MRI of chest, abdomen and pelvis to be performed until objective disease progression.
- ECG any time if clinically indicated
- Urinalysis any time if clinically indicated
- Serum or urine pregnancy test for women of childbearing potential (prior to treatment on day 1 of 1st day of study treatment). If the test is positive then a confirmatory test should be performed
- For patients with **known** BRCA status: *BRCA1/2* mutation status. 2 blood samples: One blood sample to test for *BRCA* mutations using the current commercial Myriad *BRCA* analysis test, and the second blood sample for a bridging study to validate the companion diagnostic test for olaparib
- AE and concomitant medications (including any blood transfusions) at every visit
- Patient Reported Outcomes and Quality of life questionnaire: EORTC QLQ-C30 at baseline (prior to randomisation once eligibility is confirmed), and then every 6 weeks until disease progression. CTSQ-16 every 6 weeks and at end of study treatment.

- An optional pharmacogenetic sample will be obtained from consenting patients and stored for future exploratory pharmacogenetic analysis (Section 6.7.1)
- Optional tumour biopsy at disease progression (Section 6.6.4)
- Mandatory blood sample for biomarker analysis at Day 1 and disease progression (Section 6.6.1)

Once patients have discontinued study treatment, other treatment options will be at the discretion of the investigator. Within this study chemotherapy patients will not be offered olaparib at any time.

6.2.3 Follow-up procedures

6.2.3.1 Treatment discontinuation visit due to objective radiological disease progression

Patients should be discontinued from study treatment if they have objective radiological disease progression according to RECIST (see Appendix G).

Following radiological disease progression patients will be followed for PFS2 and OS.

6.2.3.2 Treatment discontinuation visit due to any other discontinuation criteria

Patients should be discontinued from study treatment if any discontinuation criteria are fulfilled (see Section 5.8). The assessments to be carried out at the visit are detailed in the study schedule (Table 1).

Patients who have discontinued from treatment but do not have radiological disease progression will continue to be followed for PFS by RECIST assessments every 6 weeks from date of randomisation during the first 24 weeks and then every 12 weeks thereafter. Relevant PRO assessments should also continue until disease progression as per the study plan.

6.2.3.3 Patients who have objective radiological disease progression but continue on study treatment

Patients should be discontinued from study treatment if they have objective radiological disease progression according to RECIST (see Appendix G), however, patients may be allowed to continue study treatment if the investigator believes, and AZ Study Physician concurs, that the patient could continue to receive benefit, the patient is not experiencing serious toxicity, and there is no available better alternative treatment that could benefit the patient. These patients will continue study procedures as per Table 1 and will be followed for PFS2 and OS. Safety assessment can occur with the same frequency as the visits unless more frequent testing is clinically indicated.

6.2.3.4 Follow-up 30 day after last dose of study treatment (follow-up visit)

A follow-up visit should be conducted 30 days after the last dose of study treatment. Any serious and/or non-serious AEs ongoing at the time of the Discontinuation Visit or which have

occurred during the defined 30-day follow-up period must be followed-up (in accordance with Section 6.4.3). Appropriate safety evaluations should be repeated and/or additional tests performed at any time when clinically indicated, or at the discretion of the investigator, until resolution, unless, in the investigator's opinion, the condition is unlikely to resolve due to the patient's underlying disease. If the patient is lost to follow-up, then this should be noted in the eCRF. The assessments to be carried out at the 30 day follow up visit are detailed in the study schedule (Table 1).

6.2.4 Survival

Assessments for survival should be made every 8 weeks \pm 7days following objective radiological disease progression. Survival information may be obtained via telephone contact with the patient, patient's family or by contact with the patient's current physician. Survival data will be collected up to the time of the final overall survival (OS) analysis. In addition, patients should be contacted in the week following the data cut-off for the primary PFS and overall survival analyses to provide complete survival data.

Patients will be followed up as per Table 1 to the point of the final analysis. At this point investigators will be notified that no further data collection for the study is required. Monitoring and recording of SAEs will continue as per Section 6.4.4.

The status of patients at the time of an overall survival analysis should be obtained by the site personnel by checking the patients notes, hospital records, contacting the patients general practitioner and checking publicly available death registries. In the event that the patient has actively withdrawn consent to the processing of their personal data the vital status of the patient can be obtained by site personnel from publicly available resources where it is possible to do so under applicable local laws (see Section 5.9).

6.2.5 Second Progression

Following first objective progression as per RECIST, copies of the patient's radiological scans are no longer required to be sent for blinded independent central review, provided the central read confirms progression. If first objective progression is not confirmed by the central review then a further scan should be scheduled at the next RECIST visit and submitted for central review. Following first objective progression patients will be assessed every 8 weeks for a second progression (using the patient's status at first progression as the reference for assessment of second progression). A patient's progression status is defined according to local standard clinical practice and may involve any of objective radiological, symptomatic disease progression or death. RECIST measurements will not be collected for assessment of PFS2. The date of PFS2 assessment and investigator opinion of disease progression status (progressed or non-progressed) at each assessment will be recorded in the eCRF.

6.2.6 Patient management post primary PFS analysis

The data cut off date for the statistical analysis for the primary objective of the study will be established when approximately 230 confirmed progression events (~75% maturity for PFS analysis) are expected to have occurred.

Patients on study treatment at the time of the data cut-off will continue to receive study treatment until they meet any discontinuation criteria as per Section 5.8.

Patients on study treatment will be followed for core safety assessments (haematology, clinical chemistry, AEs/SAEs, concomitant medications and study treatment dosing details).

Once the primary PFS analysis has been performed the collection of RECIST data for independent central review will cease. Patients who have not had an objective disease progression at the time of the data cut off for the primary PFS analysis should continue to have RECIST assessments until first objective disease progression is determined by the investigator. RECIST assessments should be performed every 12 weeks from the last assessment prior to the data cut off date. Following first progression patients should be assessed for second progression based on radiological or symptomatic progression or death. Patients will also be followed for information on vital status to obtain the data needed for the OS analysis.

6.2.7 Patient management post final OS analysis

The data cut off date for the final statistical analysis of the study will be established when ~190 confirmed OS (~60% maturity for OS analysis) are expected to have occurred.

At this time point, the clinical study database will close to new data. Patients who are receiving treatment can either choose to discontinue from the study or where the investigator believes patients are gaining clinical benefit; patients may continue to receive study treatment. All patients will receive follow up care in accordance with standard local clinical practice.

AstraZeneca will continue to supply olaparib after completion of this study until either olaparib is licenced in that country, or it is determined that the benefit to risk profile does not support continued development of olaparib, or the national health authority has deemed the drug not approvable. In all these scenarios, AstraZeneca will work with investigators on the proper transition of patients to alternative therapies if possible.

SAEs will continue to be reported to AstraZeneca Patient Safety Department, for any patients who continue on olaparib until 30 days after study treatment is discontinued, in accordance with Section 6.4.4. Additionally as stated any SAE or non-serious adverse event, that is ongoing at the end of the study, must be followed up to resolution unless the event is considered by the investigator to be unlikely to resolve, or the patient is lost to follow-up.

After study treatment completion (i.e. after any scheduled post treatment follow-up period has ended) there is no obligation to actively report information on new AEs or SAEs occurring in former study patients. This includes new AEs/SAEs in patients still being followed up for survival but who have completed the post treatment follow up period (30 days). If an investigator learns of any SAEs, including death, at any time after a patient has completed the study, and he/she considers there is a reasonable possibility that the event is causally related to the investigational product, the investigator should notify AstraZeneca Patient Safety.

For Pharmacovigilance purposes, however, any case of MDS/AML or new primary malignancy occurring after the 30 day follow up period should be reported as a SAE (**and will generally meet at least one of the serious criteria, see section 6.4.2**) to AstraZeneca Patient Safety **regardless of investigator's assessment of causality or knowledge of the treatment arm**. A Questionnaire will be sent to any investigator reporting MDS/AML requesting detailed information on the case.

If patients who are gaining clinical benefit are allowed to continue study treatment post data cut off and / or post study completion then all SAEs must continue to be collected and reported to Patient Safety within the usual timeframe.

Drug accountability should continue to be performed until the patient stops study treatment completely.

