There have been 16 reports of myelodysplastic syndrome (MDS) and/or acute myeloid leukaemia (AML) in patients treated with olaparib as of Oct 2013; 11 cases in olaparib monotherapy trials and 5 cases in olaparib combination studies with carboplatin and paclitaxel (n=4) or cediranib (n=1). A total of 2103 patients are estimated to have received olaparib, giving a cumulative incidence of 0.76% for MDS/AML, similar to the cumulative incidence reported from control arms of olaparib randomised studies 0.7% (2/304 patients). All 16 patients had primary ovarian or peritoneal cancer and 12 of them were *BRCAl/2* positive (3 cases *BRCA* status unknown; 1 case negative). It has been hypothesised that a deficiency in the expression of *BRCA* genes may leave patients more vulnerable to the adverse effects of chemotherapy, and therefore, at an increased risk of MDS/AML as a result of cancer treatment (Cole and Strair 2010). Most patients had been treated with extensive previous chemotherapy ranging from 6 to 95 cycles over periods of 3.5 months to 15 years, including platinum agents, topoisomerase II inhibitors, alkylating agents and taxanes. The median time from diagnosis of cancer to onset of MDS was 5.3 yrs (range 2.9 -12.7). The median time from start of olaparib treatment to onset of MDS was 0.9 years (0.1 to 4.8 years). The reported events of MDS/AML occurred post discontinuation of olaparib treatment in 8 of the 16 patients following a median of 0.1 years post treatment discontinuation (range: 0.1 to 1 years). Half of the patients (n=8) had received olaparib for \leq 12 months (5 patients had \leq 6 months exposure) and the other 8 cases occurred following longer than 12 month olaparib exposure (3 patients following 12-18 months exposure and 5 patients following $>$ 2 years exposure to olaparib).

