6.4.3 Recording of adverse events

Time period for collection of adverse events

Adverse Events will be collected from time of signature of informed consent throughout the treatment period up to and including the 30-day follow-up period. However, in Screening PART 1 of the study only SAEs related to study procedures will be collected.

All ongoing and any new AEs/SAEs identified during the 30 calendar days follow up period after the last dose of study medication must be followed to resolution.

Follow-up of unresolved adverse events

Any SAEs or non-serious adverse event that is ongoing at the time of the 30-day follow up, must be followed up to resolution unless the event is considered by the investigator to be unlikely to resolve, or the patient is lost to follow up. AstraZeneca retains the right to request additional information for any patient with ongoing AE(s)/SAE(s) at the end of the study, if judged necessary.

Variables

The following variables will be collect for each AE;

- AE (verbatim)
- The date when the AE started and stopped
- Whether the AE is serious or not
- Investigator causality rating against the Investigational Product (yes or no)
- Action taken with regard to investigational product
- Outcome.

In addition, the following variables will be collected for SAEs:

- D ate AE met criteria for serious AE
- Date Investigator became aware of serious AE
- AE is serious due to
- Date of hospitalisation
- Date of discharge
- Probable cause of death
- Date of death
- Autopsy performed
- Causality assessment in relation to Study procedure(s)
- Causality assessment in relation to Other medication
- Description of AE.

Severity of AE

For each episode on an adverse event, all changes to the CTCAE grade attained as well as the highest attained CTC grade should be reported.

It is important to distinguish between serious and severe AEs. Severity is a measure of intensity whereas seriousness is defined by the criteria in Section 6.4.2. An AE of severe

intensity need not necessarily be considered serious. For example, nausea that persists for several hours may be considered severe nausea, but not a SAE. On the other hand, a stroke that results in only a limited degree of disability may be considered a mild stroke but would be a SAE.

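### Late MDS/AML and new primary malignancy must be reported in both arms, but no scheduled step asks for them and the rule is missing from the safety sections, so late ascertainment may be incomplete

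*Protocol*

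**What the plan says.** Section 1.4 lists MDS/AML and new primary malignancy among the important potential risks and says the data do not yet allow the MDS/AML relationship to be judged. On timing it reports that "The reported events of MDS/AML occurred post discontinuation of olaparib treatment in 8 of the 16 patients", at a median of 0.1 years after stopping (range 0.1 to 1 year), and that "The median time from start of olaparib treatment to onset of MDS was 0.9 years (0.1 to 4.8 years". For new primary malignancy, 16 of 19 patients were reported on treatment and 3 after stopping.

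Section 6.4.3 collects adverse events from consent "throughout the treatment period up to and including the 30-day follow-up period". Section 6.2.7 removes the duty to report new events actively after that and spells out the scope: "This includes new AEs/SAEs in patients still being followed up for survival but who have completed the post treatment follow up period (30 days". The next paragraph of 6.2.7 sets these two events apart: "any case of MDS/AML or new primary malignancy occurring after the 30 day follow up period should be reported as a SAE", irrespective of the investigator's causality view and of whether the arm is known, with a questionnaire for MDS/AML.

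Elsewhere:
- Section 5.8.1 asks for events after the 30 days only where the investigator thinks them possibly related.
- Section 6.4.3 (new cancers paragraph) treats a new primary cancer as an AE but does not extend the 30-day window. Section 6.4.4 is silent on late cases.
- Table 1 has no adverse-event entry under survival follow-up. That 8-weekly column does record subsequent therapy, second progression and survival.

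**The concern.** A duty to report a case is not a step that finds one. Once the 30-day visit has passed, a site learns of a late leukaemia or second cancer only if someone mentions it. Patients are still contacted every 8 weeks, sometimes by telephone and sometimes through family or another physician, and no item prompts the question.

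The rule that should catch these cases is also hard to find. Its text covers patients still in survival follow-up, so it applies during the trial, but it stands only under a heading about management after the final OS analysis. A site working from 5.8.1, 6.4.3, 6.4.4 and Table 1 would not meet it, and 5.8.1 gives a narrower rule that depends on perceived relatedness. In an open-label trial, a site that follows 5.8.1 alone could report late events differently in the two arms.

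What is at stake is the completeness of a randomised safety count for two named risks. The efficacy analyses are not affected.

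**Working it through.** **1. The protocol's own incidences (section 1.4).** "There have been 16 reports of myelodysplastic syndrome (MDS) and/or acute myeloid leukaemia (AML"; "A total of 2103 patients are estimated to have received olaparib, giving a cumulative incidence of 0.76% for MDS/AML"; "control arms of olaparib randomised studies 0.7% (2/304 patients".
- Olaparib: 16/2103 = 0.761%, stated as 0.76%. Reproduced.
- Control: 2/304 = 0.658%, stated as 0.7%. Reproduced.

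**2. How many earlier MDS/AML cases lay past day 30.**
- After stopping olaparib: 8/16 = 50% (exact 95% CI 25% to 75%).
- The median of 0.1 years is 0.1 × 365.25 = 36.5 days, but a figure rounded to one decimal can be anything from 0.05 × 365.25 = 18 days to 0.15 × 365.25 = 55 days. The lower end of the range, also 0.1 years, is rounded in the same way.
- At least one case, the one at 1 year, was past day 30; at most all 8 were. The figure is therefore 1 to 8 of 16, or 6% to 50%.

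**3. New primary malignancy.** After stopping: 3/19 = 16% (exact 95% CI 3% to 40%). Time since stopping is not given, so the number past day 30 is unknown.

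**4. Expected cases in this trial.** With 310 patients randomised 2:1, about 207 receive olaparib and 103 chemotherapy.
- Olaparib: 206.7 × 16/2103 = 1.6 MDS/AML cases.
- Chemotherapy: 103.3 × 2/304 = 0.7.

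**5. Upper bound on the olaparib loss, if every case past day 30 went unreported.**
- 1 of 16 late: 1.57 × 1/16 = 0.1 case; observed rate 15/2103 = 0.71%.
- 8 of 16 late: 1.57 × 8/16 = 0.8 case; observed rate 8/2103 = 0.38%.
- The true loss is smaller to the extent that sites follow the 6.2.7 rule.

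**6. Length of the routine window by arm.** Section 12.3 assumes exponential PFS, a 4-month control median and HR 0.635, so the olaparib median is 4/0.635 = 6.3 months. Assume that treatment lasts until progression; the window then closes 30 days (0.99 months) later. At the median MDS onset of 0.9 years (10.8 months), the window is still open with probability exp(−ln 2 × (10.8 − 0.99)/median):
- Olaparib: exp(−0.693 × 9.81/6.30) = 0.34.
- Chemotherapy: exp(−0.693 × 9.81/4) = 0.18.

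The mean window is median/ln 2 + 0.99, which gives about 10.1 and 6.8 months. These are shares of patients and lengths of observation, not shares of cases missed.

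**The case against.** The strongest reply is that 6.2.7 already deals with the matter. It requires any late case to be reported, in both arms, with no end date and without a causality filter, directly after the general sentence it qualifies. That stands. It rules out the reading, tempting if the no-obligation sentence is taken alone, that late MDS/AML and new malignancies are left to voluntary reports that depend on whether the investigator blames the drug. Only 5.8.1 carries such a filter, and 6.2.7 is the broader rule for these two events.

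A reader might also infer that the events will be under-counted, and unequally so. The documents do not show this. The outcome turns on how well sites follow 6.2.7, which is nowhere quantified. Nor do the complements of the window shares (66% and 82%) measure missed events: they ignore the 6.2.7 rule, deaths and permitted treatment beyond progression, and the onset time comes from patients who all had ovarian or peritoneal cancer. The latency argument is weak for new primary malignancy, where most patients were reported on treatment.

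Two further points have some weight. Anti-cancer therapy after discontinuation is recorded, so treatment for a late leukaemia or second cancer may surface that way. And with about 1.6 and 0.7 expected cases, no collection method would make the between-arm comparison informative on its own.

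None of this supplies a prompt at the 8-weekly contacts, puts the rule where sites look for safety duties, or removes the mismatch with 5.8.1.

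**Conclusion.** The point holds as a gap in ascertainment, not as a demonstrated bias. Reporting of late MDS/AML and new primary malignancy is mandatory in both arms, but it is unprompted, stands in one misplaced paragraph, and is not matched by 5.8.1. Late counts may therefore be incomplete and may differ by arm.

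The size is small in absolute terms: at most about 0.8 of 1.6 expected olaparib MDS/AML cases, and possibly as little as 0.1 even if every late case were lost. This assumes that the 0.76% incidence and the earlier timing pattern carry over to breast cancer patients. The arm difference in the routine window (34% against 18% still open at 0.9 years) further assumes that treatment duration follows the planning PFS. The direction of any imbalance cannot be derived. With so few cases expected, a single unreported one would still change the observed rate noticeably, and the remedy is cheap enough to be worth making.

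**What to change.** - Add one yes/no question, with date, on MDS/AML and on new primary malignancy at each RECIST visit after treatment has stopped and at each 8-weekly survival contact, in both arms, up to the final OS cut-off. Show it in Table 1 and provide it in the eCRF.
- Carry the late-reporting rule from 6.2.7 into 6.4.3 and 6.4.4, and reconcile 5.8.1 with it so that these two events are not subject to a relatedness judgement.
- Tabulate these events by arm regardless of time since last dose, unless the SAP, which is not at hand, already provides for this.

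The cost is a protocol amendment, one eCRF field and a slightly higher SAE count. No visit or procedure is added.
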